Study Protocol with SAP

Date: 21.1.2023

Effects of family-based treatment on adolescent outpatients treated for anorexia nervosa in the Eating Disorder Unit of Helsinki University Hospital

[name],^{1*} [name],¹ [name],² [name]^{1,3,4}

1 Departement of Psychiatry, University of Helsinki and Helsinki University Hospital, [name];

2 Psychiatric hospital, City of Helsinki, [name];

3 Department of Psychology and Logopedics, Faculty of Medicine, [name];

4 Department of Psychology, Åbo Akademi University, [name]

* Point of contact

[name]
Eating disorder unit
[name]
Helsinki
Finland
[contact]
[name]

Study design

The study was conducted at the outpatient department of the Eating Disorder Unit, which is a tertiary health care unit at Helsinki University Hospital's Psychiatry Department. The unit provides specialized assessment and treatment for adolescents and adults with severe eating disorders in the Helsinki region, with around 1.6 million inhabitants. At the unit, most treatment is provided at an outpatient level, but day patient and inpatient treatments are also available.

The study plan was approved by the Ethics Committee of Helsinki University Hospital before the beginning of the data collection. Patients and their guardians received information about the study both orally and in a cover letter. The participants were assured of the confidentiality and anonymity of the data and of the voluntary nature of participation. The patients and their guardians gave written confirmation of their consent.

Data for the study was gathered from the medical records of the patients at the end of treatment.

Participants

The participants and their parents were recruited from June 1, 2013, through December 31, 2017. All outpatients aged 13–18 years meeting the diagnostic criteria for Anorexia nervosa (AN) and admitted to the Family based treatment (FBT) at the Eating Disorder Unit of Helsinki University Hospital were invited to participate in the study. During the study period, 428 adolescent patients started outpatient treatment at the Eating Disorder Unit. Of those, 52 female patients diagnosed with AN, with a mean age of 14.50 ($SD = 1.31$) years, were admitted to FBT, and all of them participated in the study. The mean BMI at the beginning of treatment was 16.42 ($SD = 1.48$). On average, the participants had suffered from eating disorder symptoms for 13.29 ($SD = 8.15$) months before FBT started.

Intervention

On the patient's first visit to the unit, the attending psychiatrist usually makes a clinical decision of whether FBT is suitable for the patient. The decision is based on an assessment of the patient's medical and mental state, compliance to treatment, and family functioning. At the unit, FBT is carried out by a family therapist who has received FBT training. The duration of FBT is commonly 6–12 months, in most cases comprising 10–20 sessions. At the beginning of treatment, there are weekly sessions; later in treatment, the sessions are less frequent. The patient and their family meet their psychiatrist every four to six weeks, and the family therapist also takes part in these meetings. The treatment is implemented in accordance with the FBT treatment manual, but in a few cases, the FBT protocol was modified to have an increased number of sessions and longer duration due to the patient's clinical condition.

Treatment characteristics

The number of FBT treatment sessions ranged from 5 to 40 (*Mean* = 15.3, *SD* = 7.34). In 11 cases (21.2%), the treatment demanded more than 20 sessions. The treatment lasted up to 23 months, with an average duration of 10.25 (*SD* = 5.0) months. In all cases but one, FBT was finished in accordance with the clinical situation and treatment plan, and only one family dropped out of treatment. This withdrawal happened after session 10 of FBT when the family decided to continue the treatment at a private clinic. As the participant had participated in half of the planned FBT sessions before dropping out and had achieved change in weight and eating disorder symptoms, we did not exclude her from the study.

Assessments

Pre-treatment information about the patients' growth and health before eating disorder onset, as well as diagnostic evaluations of comorbid psychiatric disorders, was gathered from their medical records. Assessment at baseline and at the end of treatment (EOT) included weight, height, eating

disorder symptoms, and psychopathology. According to FBT protocol, weight was assessed before every treatment session. The participants were weighed in their underwear on a balance beam scale that was regularly re-calibrated. According to the World Health Organization's (WHO) definitions, normal body weight was defined as a BMI ≥ 18.5 .

The attending psychiatrists' assessments of eating disorder symptoms and psychopathology at baseline and at EOT were used. The participants' caregivers, as well as their therapist, had a chance to express their opinion regarding whether the patient benefited from FBT or not.

Statistics

The statistical analyses were performed using IBM SPSS Statistics 25. First, the data was analyzed for descriptive parameters and incidence rates of all the variables. According to skewness and kurtosis, the data was mostly normally distributed. To assess treatment outcomes, the change in BMI was tested using a two-way analysis of variance for repeated measures, and the McNemar chi-square test was used to analyze the change in the incidence rates of symptoms. Further, for comparing groups of patients at EOT, Student's *t*-test and chi-square tests were used. All analyses were two-tailed. The alpha level was set at $p \leq 0.05$. We also calculated Cohen's *d* to estimate the effect sizes of statistically significant differences in the *t*-test, interpreting an effect size of 0.2 to 0.5 as small, 0.5 to 0.8 as medium, and over 0.8 as large. For the chi-square test, the phi (ϕ) coefficient was a measure for the effect size. A value of 0.1 was considered a small effect, 0.3 a medium effect, and 0.5 a large effect.

Results

At EOT, a majority (73.1%) had achieved a normal body weight [body mass index (BMI) ≥ 18.5]. Participants with a BMI ≥ 18.5 at EOT had a significantly higher pre-treatment BMI than those with BMI < 18.5 at EOT. Participants with a BMI ≥ 18.5 at EOT showed significantly higher total weight gain during the treatment period, a significantly higher rate of regular menstrual period at EOT,

significantly lower rates of dietary restrictions, and less cognitive or behavioral symptoms of the eating disorder overall, compared to participants who did not achieve a normal body weight. In 22 cases (42.3%), there was no need for further treatment at the end of FBT. Participants who needed further treatment after FBT, compared to those who did not, showed significantly higher rates of psychiatric comorbidity, history of mental health treatment, and need for psychopharmacological treatment.

Competing interests

The authors declare no conflict of interest

List of abbreviations

AN = Anorexia nervosa

BMI = body mass index

EOT = end of treatment

FBT = Family-based treatment

WHO = World Health Organization

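### Does the word Effects in the title of a single-group FBT series call for a change to the plan?

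*Combined protocol and SAP*

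**What the plan says.** The title reads "Effects of family-based treatment on adolescent outpatients treated for anorexia nervosa".

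Under Participants, only patients already admitted to FBT were invited. The sample is "52 female patients diagnosed with AN", who "were admitted to FBT, and all of them participated in the study". They come from 428 adolescents who began outpatient treatment at the unit in the recruitment period.

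Under Intervention, "the attending psychiatrist usually makes a clinical decision of whether FBT is suitable for the patient". The judgement rests on medical and mental state, treatment compliance and how the family functions. The same section adds "The patient and their family meet their psychiatrist every four to six weeks", with the family therapist present.

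Under Treatment characteristics, "The number of FBT treatment sessions ranged from 5 to 40", and "The treatment lasted up to 23 months, with an average duration of 10.25" months. Study design notes that at the unit "day patient and inpatient treatments are also available".

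The Statistics section tests BMI change by a repeated-measures two-way ANOVA and symptom change by McNemar's test. It compares groups of patients at end of treatment (EOT) by t-tests and chi-square tests. The Results give EOT rates and compare patients by EOT BMI and by need for further treatment. No discussion or limitations section follows.

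**The concern.** In a trial document, Effects is normally read causally: the BMI and symptom changes happened because of FBT. That reading needs a contrast with patients who did not have FBT, and none is described. Three other explanations are open.

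- **Natural course.** Treatment averaged 10.25 months and ran up to 23, which is long enough for change unrelated to FBT.
- **Selection.** The suitability criteria are plausibly prognostic. The Results themselves show that patients with a higher pre-treatment BMI more often reached normal weight, and that comorbidity and earlier mental health treatment went with needing more care.
- **Other care.** The psychiatrist meetings, any drug treatment, and day-patient or inpatient care might have contributed.

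If the literal reading held, a reader could take the 73.1% at normal weight as the yield of FBT, and could expect it in patients who would not have been judged suitable. Nothing next to the Results warns against this.

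**Working it through.** **1. Is there any contrast with and without FBT?** Inputs: 52 participants (Participants) and a minimum of 5 sessions (Treatment characteristics). Participants without FBT = 52 − 52 = 0. Each analysis in turn:

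| Analysis (Statistics, Results) | What is compared | FBT versus no FBT? |
|---|---|---|
| Repeated-measures two-way ANOVA on BMI | Time, plus a second factor that is not named | No; the second factor cannot be FBT versus none |
| McNemar test on symptoms | Same patients, baseline and EOT | No |
| t-test and chi-square | EOT BMI at or above 18.5 versus below; further treatment needed versus not | No; both sides had FBT |

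So the factual core of the concern is right.

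**2. Do the stated rates reproduce?** The count behind 73.1% is not printed. 38/52 = 73.08%, while 37/52 = 71.15% and 39/52 = 75.00%, so 38 is the only count that fits. For the second rate, 22/52 = 42.31%, stated as 42.3%. Both agree.

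**3. Can the size of an FBT effect, or of the bias, be found?** The difference would be 73.1% minus the rate without FBT, and the document gives no such rate. Purely as an assumption, let that rate run from 40% to 70%:

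| Assumed rate without FBT | 38/52 minus that rate |
|---|---|
| 40% | +33.1 points |
| 50% | +23.1 points |
| 60% | +13.1 points |
| 65% | +8.1 points |
| 70% | +3.1 points |

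The answer runs from large to near nil on a figure that the document does not supply. The mean of 13.29 months of symptoms before FBT (Participants) is the only information on earlier course. It does not rule out spontaneous change.

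**4. Is other care during FBT shown?** No.
- The psychiatrist meetings stand under Intervention and the family therapist attends them, so they may be part of the treatment package.
- Need for psychopharmacological treatment appears only in the comparison of patients who did and did not need care after FBT, without numbers or timing.
- Day-patient and inpatient care is a description of the unit. Its use by the 52 is not stated.

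Other care cannot be excluded, but it is not documented either.

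**5. Where does the document assert causation?** The title does. Two phrases lean slightly that way: Statistics speaks of assessing treatment outcomes, and Assessments mentions opinions on whether the patient benefited. The Results sentences say what proportion reached a BMI threshold and which groups differed. None says that FBT produced the change.

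**6. What would an edit alter?** With Outcomes of in place of Effects of, and a sentence of caution beside the Results, the tests, the alpha level, 38/52, 22/52 and the group comparisons are all unchanged.

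**The case for a change.** The best case for acting is that titles are what readers and indexes carry forward, that this document reports results and is therefore more than a plan, and that the remedy costs a few words. The selection is disclosed but never tied to how the results should be read, and the study's own associations suggest that selection could matter. If the Results are already descriptive, the title is the outlier and bringing it into line is easy.

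Much of this stands. The title is looser than the design, and Outcomes of would be the better wording. The missing link between selection and interpretation is also real.

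What does not stand is the step from there to a change in the plan. A reader who reaches Participants and Intervention sees a single treated group chosen largely on clinical judgement, with the criteria listed. The document is a protocol with SAP carrying a short results summary, so interpretive caution would ordinarily sit in the study report, which is not available here. Its absence from this text is weak evidence of a causal claim. Confidence intervals on the two EOT rates would describe sampling error only and would not touch causation or selection. The all-female sample is stated plainly under Participants and need not be in the title.

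**Conclusion.** No change to the plan is needed. The observation is correct as far as it goes: with 0 of 52 participants untreated, the pre-post tests describe change during FBT in patients selected for it and do not estimate what FBT caused. But the overstatement is essentially one title word, the reported findings do not repeat it, and the design facts needed to read them properly are in the document. Correcting the word would move no estimate, test or stated result, and would not make the bias any more knowable. The point therefore falls as an editorial preference without statistical gain.

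This rests on two assumptions: that no comparison group exists beyond what the document describes, and that causal interpretation is left to the study report. If that report presented the 73.1% or the BMI change as the effect of FBT, that would be a fair criticism of the report.

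### Student's t-test assumes equal variances, the EOT BMI groups are 38 and 14, and no variance check is reported: Welch's test is a cheap, minor improvement

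*Combined protocol and SAP*

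**What the plan says.** The Statistics section assigns repeated-measures analysis of variance and McNemar's test to treatment outcomes. It then turns to group comparisons: "Further, for comparing groups of patients at EOT, Student's *t*-test and chi-square tests were used". The one statement about assumptions is "According to skewness and kurtosis, the data was mostly normally distributed". On error control it says "All analyses were two-tailed. The alpha level was set at" p ≤ 0.05.

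The Results section defines the main grouping: "At EOT, a majority (73.1%) had achieved a normal body weight". Two continuous variables are then reported as differing between the BMI groups. Participants at or above 18.5 "had a significantly higher pre-treatment BMI than those with BMI < 18.5 at EOT", and they "showed significantly higher total weight gain during the treatment period, a significantly higher rate of regular menstrual period at EOT". A second grouping is by need for further treatment: "In 22 cases (42.3%), there was no need for further treatment at the end of FBT". Every difference named for that grouping is a rate.

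The document mentions no check of equal variances, no unequal-variance test and no SD by EOT group. The only BMI SD is the whole-sample baseline value, 1.48 (Participants section). The text does not link individual tests to individual variables. I assume that the t-test was used for pre-treatment BMI and weight gain.

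**The concern.** Student's test pools the two group variances, and the pooled figure is dominated by the larger group. When the groups differ in size, the pooled standard error is wrong if the spreads differ. If the smaller group has the larger spread, the standard error and the p-value are too small; if it has the smaller spread, both are too large. Skewness and kurtosis describe the shape of a distribution and say nothing about whether two groups share a variance.

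What is at stake is narrow. Weight gain is tied to the grouping by construction, because ending above 18.5 depends on how much was gained, so its p-value carries little information. That leaves mainly the p-value for pre-treatment BMI. The chi-square, McNemar and repeated-measures analyses are not touched by this point.

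**Working it through.** **Group sizes.** Inputs: N = 52 (Participants section), with the one family that left treatment kept in (Treatment characteristics section), and 73.1% at or above 18.5 (Results section). 37/52 = 71.2%, 38/52 = 73.1%, 39/52 = 75.0%. Only 38 fits, which leaves 14. For the second grouping, 22/52 = 42.3%, which leaves 30.

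**Effect of unequal spread.** Let r be the SD of the group of 14 divided by the SD of the group of 38, with the latter set to 1. The documents give no group SDs, so r is varied as an assumption.

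- Pooled variance: (37 + 13r²)/50
- Student's standard error: √[pooled variance × (1/38 + 1/14)]
- Correct standard error: √(1/38 + r²/14)

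Example at r = 1.5: pooled variance = (37 + 13 × 2.25)/50 = 1.325, Student's standard error = 0.360, correct standard error = 0.4325. A Student t of 2.009 (p = 0.05 on 50 df) becomes a Welch t of 2.009 × 0.360/0.4325 = 1.67 on about 17.4 df, p = 0.11.

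Size was simulated with normal data, two-sided nominal 5%, 1,000,000 replicates per ratio. The last column converts a Student p of exactly 0.05, as in the example.

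| r (assumed) | Student's size, 38 vs 14 | Welch p when Student p = 0.05 |
|---|---|---|
| 0.5 | 1.0% | 0.010 |
| 2/3 | 2.0% | 0.021 |
| 0.8 | 3.1% | 0.034 |
| 1 | 5.0% | 0.056 |
| 1.25 | 7.6% | 0.086 |
| 1.5 | 10.2% | 0.11 |
| 2 | 14.3% | 0.15 |

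Welch's size stays at 5.0% to 5.1% throughout. With 30 vs 22 and the same ratios (group of 22 over group of 30), Student's size runs only from 3.3% to 7.6%.

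**Which ratios does the grouping itself suggest?** As a benchmark, suppose that EOT BMI and the compared variable are bivariate normal, and cut EOT BMI at its 14/52 = 26.9th percentile (z = −0.615, normal density φ = 0.330).

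- Remaining variance of EOT BMI, lower group: 1 − zφ/0.269 − (φ/0.269)² = 0.250 of the original
- Upper group: 1 + zφ/0.731 − (φ/0.731)² = 0.518
- For a variable with correlation c to EOT BMI: r = √{[1 − c²(1 − 0.250)] / [1 − c²(1 − 0.518)]}

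For pre-treatment BMI, c is the baseline–EOT correlation, assumed to lie between 0 and 0.7, so r runs from 1.00 down to 0.91. For BMI gain (standing in for weight gain), I use the documented baseline SD of 1.48, an assumed EOT SD s of 1.0 to 2.0 and the same correlations. The largest c is at zero correlation and s = 2.0: 2.0/√(2.0² + 1.48²) = 0.80, giving r = 0.865. So r runs from about 0.87 to 1.00. Student's size at r = 0.865 is 3.65% (2,000,000 replicates), so the range is about 3.7% to 5.0%. At r = 0.865 a Student p of 0.05 becomes a Welch p of 0.041; at 0.91 it becomes 0.046.

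Under this benchmark, no true difference in pre-treatment BMI means c = 0 and r = 1, where Student's size is exactly 5%.

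**Price of Welch if the variances are equal** (38 vs 14, power of Student vs Welch): 34.8% vs 33.5% at d = 0.5, 71.0% vs 68.9% at d = 0.8, 96.4% vs 95.6% at d = 1.2. The losses are 1.3, 2.1 and 0.8 points.

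**The case against.** The strongest reply is that this is an unreported check and not a demonstrated fault. The only scenario tied to the documents' own figures, the benchmark, leaves Student's test nominal or slightly conservative. In that model any non-zero correlation with EOT BMI pushes the SD ratio below 1, the side on which Student's p-value tends to be too large. That stands, and it limits the weight of the point. The benchmark is still a model, with correlations and an EOT SD that the documents do not give.

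A reader might infer from the table that the pre-treatment BMI finding carries a false-positive risk of 10% to 14%, or that it would lose significance under Welch. The documents do not support either reading. Those sizes need an SD in the group of 14 that is 1.5 to 2 times that in the group of 38, and nothing in the text suggests it. The Results section gives no p-values, so the distance from 0.05 is unknown as well.

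Three further replies are fair. Student's may be loose wording for a version that allows unequal variances. A variance check or group SDs may exist and simply be absent from a short narrative. And the document already contains results, so the change is a re-run and not a prospective choice. All three stand. They lower the severity, but none makes Student's the better test at 38 vs 14.

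**Conclusion.** The point holds as a minor improvement. The named test rests on an equal-variance assumption that the reported check does not cover, and it is applied to groups of 38 and 14, where that assumption matters. The direction and size of any error are unknown: about 3.7% to 5.0% under the benchmark, and 1.0% to 14.3% across the assumed SD ratios of 0.5 to 2. The reach is essentially one p-value, that for pre-treatment BMI. The named differences by need for further treatment are all rates, so no reported t-test is visible there.

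This rests on four assumptions: no missing EOT BMI, the t-test being the one used for the two continuous variables, an equal-variance version having been run, and normal data in the simulations.

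**What to change.** Name Welch's t-test for the continuous comparisons by EOT BMI group, re-run pre-treatment BMI and total weight gain on the data in hand, and report each group's mean and SD. The SDs also help a reader interpret the Cohen's d values that the Statistics section promises. If an unequal-variance version was already used, say so; only the SDs are then needed.

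Use Welch outright and do not make it conditional on a preliminary variance test. At 38 vs 14, a simulated Levene test detected an SD ratio of 1.5 only about 40% of the time.

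The cost is one wording change and a short re-run, with about 1 to 2 points of power lost if the variances are in fact equal. No new data are needed.

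### Cohen's d is calculated only for significant t-tests and without intervals, so at 38 vs 14 an observed |d| below 0.63 gets no d

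*Combined protocol and SAP*

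**What the plan says.** The Statistics section of the combined protocol and SAP names Student's t-test and chi-square tests "for comparing groups of patients at EOT", two-tailed, with alpha 0.05. Under its effect-size rule, Cohen's d serves "to estimate the effect sizes of statistically significant differences in the" t-test. The bands by which a value of d is to be read are also given there: "interpreting an effect size of 0.2 to 0.5 as small, 0.5 to 0.8 as medium, and over 0.8 as large". The measure named for chi-square comparisons is phi, and no significance condition is attached to it; the text says only that this "coefficient was a measure for the effect size". The section mentions no confidence intervals.

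The Results section states: "At EOT, a majority (73.1%) had achieved a normal body weight". It names two continuous comparisons across that split. Participants who reached BMI ≥ 18.5 "had a significantly higher pre-treatment BMI than those with BMI < 18.5 at EOT", and they "showed significantly higher total weight gain during the treatment period". A second split, by need for further treatment, is 22 vs 30; the differences named for it are all rates. The Results section prints no value of d for any comparison.

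**The concern.** Reporting an effect size only when p ≤ 0.05 makes the test result decide which estimates the reader sees. This has two consequences. First, the smaller estimates get no d, although with only 14 patients in one group a non-significant result says little about the size of a difference. Second, the d values that are reported have been selected for being large, so they overstate modest true effects on average. Phi carries no such condition, and no reason is given for treating the two measures differently.

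What is at stake is how the secondary group comparisons are read. The tests themselves are not affected.

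**Working it through.** **Inputs.** Total 52 (Participants). The Results section gives 73.1% with BMI ≥ 18.5. Since 37/52 = 71.2%, 38/52 = 73.1% and 39/52 = 75.0%, the split must be 38 vs 14. The second split is 22 vs 30 (Results). Two-sided alpha is 0.05 and the test is Student's t (Statistics). Two assumptions are needed because the documents are silent: d is standardised by the pooled SD, and data are complete. The plan states no power or minimum d, so there is no design figure to reproduce.

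**Smallest d that can be reported.** For Student's t with a pooled SD, d = t × √(1/n1 + 1/n2). The critical t on 50 degrees of freedom is 2.0086.

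- 38 vs 14: 2.0086 × √(1/38 + 1/14) = 2.0086 × 0.3126 = 0.628.
- 22 vs 30: 2.0086 × √(1/22 + 1/30) = 0.564.

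Both floors lie above 0.5, so a d in the small band cannot be reported in either split. At 38 vs 14 only about 0.63 to 0.8 of the medium band can appear. Missing values would raise the floor, for example to 0.65 at 36 vs 13.

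**Selection at 38 vs 14.** The true d values below are assumed, because the documents give no group means, group SDs or d values. The chance of getting a d is the power from the noncentral t with 50 degrees of freedom. The means were simulated from the same distribution.

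| Assumed true d | Chance of getting no d | Mean d, unfiltered | Mean \|d\| once filtered | Filtered mean / truth |
|---|---|---|---|---|
| 0.5 | 65% | 0.508 | 0.85 | 1.70 |
| 0.8 | 29% | 0.812 | 0.97 | 1.21 |
| 1.0 | 12% | 1.015 | 1.09 | 1.09 |
| 1.2 | 4% | 1.219 | 1.24 | 1.04 |
| 1.5 | 0.3% | 1.523 | 1.53 | 1.02 |

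An unfiltered d is itself about 1.5% high at this sample size, so almost no selection bias is left at 1.2 to 1.5.

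**What an interval would add at 38 vs 14** (95% CI for d by inverting the noncentral t):

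- Observed 0.10: −0.51 to 0.71. No d under the rule; the plan's large range (over 0.8) is excluded.
- Observed 0.5: −0.12 to 1.12, p = 0.12. No d under the rule; compatible with no effect or a large one.
- Observed 0.8: 0.16 to 1.43, p = 0.01. A d is given, but no interval is planned.

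The first two cases are treated alike under the rule although they support different conclusions.

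**The case against.** The strongest reply is that the rule has no identifiable victim. Pre-treatment BMI and total weight gain were both significant, so each qualifies for a d, and removing the condition would leave those two values exactly as they are. The differences named for the 22 vs 30 split are rates, to which d does not apply. All of this stands. The suppression part concerns only non-significant t-tests that the documents do not show.

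A reader might also infer that the d values reported from this study are inflated. The documents do not support that. The bias is an average over repeated samples and depends on a true effect that is unknown. For weight gain the groups are defined by BMI at the end of treatment, to which weight gain contributes directly, so a sizeable true difference, where the bias is small, is plausible.

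Nor does the rule by itself make the size of a non-significant difference unknowable. At fixed group sizes |d| = 0.3126 × |t|, so an exact p-value, a t statistic, or group means and SDs would give |d| and its interval. The reader would have to do that calculation, and could not if only a statement of non-significance were printed. The documents do not say which would be reported. The absence of d values from the Results section proves nothing either way: it is a short summary that prints no d, phi, p-value or interval for any group comparison.

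**Conclusion.** The point holds as a minor one. The plan states a rule that ties the reporting of Cohen's d to significance. Under Student's t, a pooled SD and complete data, the rule withholds d for any observed |d| below 0.63 at 38 vs 14 and below 0.56 at 22 vs 30. It makes reported values too high on average where the true effect is modest (1.7 times at an assumed 0.5, 1.2 times at an assumed 0.8), with little bias above about 1.2.

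For the two named continuous comparisons the gain from a change is the interval alone. A reader might take the empty small band as a fault in the plan's bands; it follows from the filter and the group sizes, and the bands themselves are not in question. The chi-square comparisons are not criticised, since phi has no stated filter. No p-value, repeated-measures result or McNemar result changes.

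**What to change.** In the Statistics section, delete the restriction of Cohen's d to significant differences. State that the mean difference and Cohen's d, each with a 95% CI, are reported for every t-test group comparison whatever the p-value.

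This needs no new data, only the group means, SDs and counts. The cost is a few more table columns and intervals that will be wide, especially with 14 patients in one group.

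### Weight gain is tested between groups formed by end-of-treatment BMI, so the significant difference is largely built in, and the split cannot show whether gain varies with baseline BMI

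*Combined protocol and SAP*

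**What the plan says.** The Statistics section plans Student's t-test and chi-square tests "for comparing groups of patients at EOT", two-tailed at 0.05, with Cohen's d "to estimate the effect sizes of statistically significant differences". The Results section forms the groups at an EOT BMI of 18.5: "At EOT, a majority (73.1%) had achieved a normal body weight". It then reports two significant differences that matter here:

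- Weight gain: "Participants with a BMI ≥ 18.5 at EOT showed significantly higher total weight gain during the treatment period".
- Baseline BMI: "Participants with a BMI ≥ 18.5 at EOT had a significantly higher pre-treatment BMI than those with BMI < 18.5 at EOT".

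The treatment outcome is analysed separately: "To assess treatment outcomes, the change in BMI was tested using a two-way analysis of variance for repeated measures". The second factor of that analysis is not named. No model of gain or attained BMI on baseline BMI is described, and nothing warns the reader that gain is part of the grouping variable.

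**The concern.** A between-group test is informative when the tested variable could plausibly be equal in the two groups. Here it could hardly be. Among patients with the same baseline BMI and height growth, those above the cut at EOT are exactly those who gained more. The significant gain result therefore mostly restates how the groups were made, but it is listed beside comparisons that do carry information, such as menstruation and dietary restriction.

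The split also leaves a useful question open. Patients start at different distances from a fixed cut, so a higher baseline BMI among those who reach 18.5 does not show whether they gained more or less than others. The documents do not claim that it does. Still, a reader who sees higher baseline BMI and higher gain side by side could infer that heavier patients respond better, and the two results do not support that.

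**Working it through.** **Inputs from the documents.** n = 52 and baseline BMI mean 16.42, SD 1.48 (Participants); cut at 18.5 (Assessments); 73.1% at or above it (Results); two-sided 0.05 (Statistics).

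**Reproducing the split.** 38/52 = 73.1% (37/52 = 71.2%, 39/52 = 75.0%), so the groups are 38 and 14.

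**Distance to the cut, from the documents alone.**
- 1 SD above the mean: 16.42 + 1.48 = 17.90, which needs 18.5 - 17.90 = 0.60 BMI units.
- 1 SD below the mean: 16.42 - 1.48 = 14.94, which needs 18.5 - 14.94 = 3.56 BMI units.

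**Assumptions.** Normality; SD of BMI gain (SDg) of 1.0, 1.5, 2.0 or 2.5; baseline-gain correlation r of +0.3, 0, -0.3 or -0.5; mean gain set so that 38/52 are expected to reach 18.5. The documents give neither SDg nor r.

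**Difference created by the split.** Since EOT BMI = baseline + gain, Cov(gain, EOT) = SDg² + r × 1.48 × SDg. Splitting EOT BMI at the point that leaves p = 38/52 above gives

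expected gain difference = [φ(z) / (p(1-p))] × (SDg² + r × 1.48 × SDg) / SD(EOT),

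with SD(EOT) = √(1.48² + SDg² + 2r × 1.48 × SDg), z = 0.615, φ(z) = 0.330 and φ(z)/(p(1-p)) = 1.678.

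Example, SDg = 1.5 and r = 0: SD(EOT) = √(2.1904 + 2.25) = 2.107, so 1.678 × 2.25/2.107 = 1.79 BMI units.

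The difference is zero only if r = -SDg/1.48. That is -0.68 for SDg = 1.0; for SDg above 1.48 no correlation achieves it.

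**Simulation.** 100,000 cohorts of 52 per cell, pooled t-test, counted when significant in the reported direction. Entries are for SDg = 1.0 / 1.5 / 2.0 / 2.5.

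| r | Expected gain difference (BMI units) | Gain significant (%) | Gain and baseline BMI both significant (%) |
|---|---|---|---|
| +0.3 | 1.20 / 2.04 / 2.91 / 3.78 | 99 / 100 / 100 / 100 | 99 / 100 / 100 / 98 |
| 0 | 0.94 / 1.79 / 2.70 / 3.61 | 89 / 99 / 100 / 100 | 89 / 98 / 93 / 82 |
| -0.3 | 0.61 / 1.51 / 2.49 / 3.46 | 51 / 93 / 100 / 100 | 51 / 85 / 62 / 35 |
| -0.5 | 0.33 / 1.28 / 2.35 / 3.39 | 18 / 82 / 99 / 100 | 18 / 60 / 28 / 8 |

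Median simulated Cohen's d for gain is 1.04 to 1.89 at r = 0, 0.64 to 1.76 at -0.3 and 0.34 to 1.71 at -0.5. The Statistics section calls anything over 0.8 large. The documents report no d for gain.

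**Can the reported pair identify the baseline-gain relation?** At r = 0 the pair appears in 82 to 98% of cohorts although gain is unrelated to baseline. At r = -0.3, 20/46/28/11% of cohorts show the pair together with significantly greater gain in patients with lower baseline BMI. At r = +0.3, 59% in each cell show the pair together with significantly greater gain in those with higher baseline BMI. The same two sentences therefore fit a relation of either sign, or none.

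**Robustness.** Fixing the split at exactly 38/14 gives gain significant in 90-100%, 51-100% and 18-100% at r = 0, -0.3 and -0.5. Working in kilograms (assumed height 1.63 m, SD 0.06, growth about 1 cm) gives 88-100%, 51-100% and 19-100%.

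**The case against.** The strongest objection is that the result is not automatic, and that the other reported finding rules out part of the grid. At r = -0.5 a significant baseline difference is common only when the SD of gain is small, and with SDg = 1.0 gain is significant in only 18% of cohorts. In that corner a significant gain result would be informative. A negative correlation cannot be excluded either, because treatment length followed the clinical course. This is why the difference is called largely, and not wholly, built in. It does not rescue the test: among cohorts with a significant baseline difference, gain is also significant in 77 to 100% in every cell of the grid except SDg = 1.0 with negative correlation (51% at -0.3, 18% at -0.5).

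A second objection is that baseline BMI is equally a component of EOT BMI, so it is inconsistent to let that comparison stand. The difference is timing. Baseline BMI precedes the outcome and is a legitimate predictor of reaching 18.5; gain is part of the outcome itself.

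Third, the documents never claim that gain depends on baseline BMI. That is correct. The second half of the point is a limit of the split, not a contradiction of a stated conclusion.

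Fourth, the unnamed second factor of the repeated-measures ANOVA matters. If it were EOT group, its group-by-time interaction would share the same dependence. The overall change over time would not, and only that part is treated here as unaffected.

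**Conclusion.** The concern holds and should be fixed. One reported significant result mostly restates the grouping, and the text does not say so. How strongly it is forced rests on the assumed SD of gain and baseline-gain correlation: close to certain at a correlation of 0 or above, and weak only where the SD of gain is small and the correlation clearly negative. The direction of the argument needs only the identity that EOT BMI is baseline plus gain, with height growth a minor departure.

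The 73.1% rate, the overall BMI and symptom changes, the menstruation, dietary-restriction and symptom comparisons, and the further-treatment comparison do not change.

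**What to change.** 1. Report weight gain by EOT-BMI group descriptively, with no significance test or Cohen's d, and say that gain is a component of the grouping. Keep the pre-treatment BMI sentence as an association with reaching 18.5.
2. Add one linear regression of continuous EOT BMI on baseline BMI, with age, in all 52 patients. Report the baseline slope with its 95% CI, read against 0 for attained BMI and against 1 for gain (a slope of 1 means gain is unrelated to baseline BMI at a given age).
3. Name the second factor of the repeated-measures ANOVA. If it is EOT group, treat its interaction with time as in item 1.

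In simulation (20,000 cohorts per cell, with assumed baseline-age correlations of 0, 0.3 and 0.5 and an age effect of 0 or 0.3) the CI covered a true slope of 0 or 1 in 94.7 to 95.4% of cohorts, with half-width 0.18 to 0.55. With no age effect, the test against 1 rejected in 46 to 59% at r = -0.3 and 92 to 97% at -0.5, so the interval should be reported and not only a p-value. Baseline BMI error of SD 0.2 to 0.3 (assumed) would pull a slope of 1 to about 0.98 to 0.96.

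The cost is one model on data already held ("Assessment at baseline and at the end of treatment (EOT) included weight, height", plus age), one reworded sentence and one withdrawn p-value.
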